3.5. Discontinuation Criteria

Subjects may be withdrawn from the study under the following circumstances:

- The subject withdraws consent to participate in the study
- The subject permanently discontinues idelalisib treatment for any reason
- The subject experiences a toxicity that necessitates permanent discontinuation of idelalisib treatment
- The subject has progressive disease
- The subject does not comply with the requirements of the protocol (eg initiation of a non-protocol anti-tumor treatment)
- Gilead, a regulatory agency, or an independent ethics committee (IEC) discontinues the study

The reason for withdrawal will be recorded in the eCRF.

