4.3. Exclusion Criteria

Subjects who meet *any* of the following exclusion criteria are not eligible to be enrolled in this study:

- 1) Known hypersensitivity or intolerance to any of the active substances or excipients in the formulation of idelalisib.

- 2) Toxicities that would preclude initiating therapy with idelalisib prior to enrollment
(eg history of drug-induced pneumonitis, ongoing inflammatory bowel disease)
- 3) Concurrent participation in another therapeutic clinical trial.
- 4) Pregnant or breastfeeding.
- 5) Ongoing infection, treatment, or prophylaxis for CMV within the past 28 days.

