5.2.10. Idelalisib Dose Adjustments

The dose adjustment recommendations and requirements in [Table 5-2](#) are based on the Common Terminology Criteria for Adverse Events (CTCAE) grade of specific toxicities. However, exceptions are expected for subjects who initiate study treatment with low blood counts. Clinical judgment should apply, and in cases of uncertainty, the study medical monitor should be contacted.

The dose modification instructions in [Table 5-2](#) focus on the types of events most commonly associated with idelalisib. The modifications include both recommended and required actions. When a modification is indicated as a recommendation, it serves as a guideline; variations from the recommendation may be warranted based on an investigator's individual judgment in considering potential risks, benefits, and therapeutic alternatives available to each subject.

Table 5-2. Dose Adjustment Guidelines {Gilead Sciences Inc 2014}

NCI CTCAE Grade ^a	Idelalisib
HEMATOLOGICAL ADVERSE EVENTS	
Neutropenia	
Grade \leq 2 neutropenia	Recommended Action: Maintain current dose level and schedule.
Grade \leq 3 neutropenia	Required Action: Monitor blood counts at least weekly until ANC \leq Grade 2. Recommended Action: Maintain current dose level and schedule.
Grade 4 neutropenia (or occurrence of neutropenic fever or infection)	Required Action: 
Withhold idelalisib.Monitor blood counts at least weekly until ANC \leq Grade 2 Recommended Action: 
May resume idelalisib at lower dose level when ANC grade is \leq Grade 3Neutropenia should be managed according to established clinical guidelines.
Thrombocytopenia	
Grade \leq 3	Recommended Action: Maintain current dose level and schedule.
Grade 4	Required Action: Withhold idelalisib for bruising or bleeding until Grade \leq 3. Recommended Action: May resume idelalisib at initial or reduced dose level at investigator discretion.
NON-HEMATOLOGICAL ADVERSE EVENT	
Rash	
Grade \leq 1	Recommended Action: Maintain current dose level and schedule
Grade 2	Recommended Action: Maintain current dose level and schedule
Grade \geq 3	Required Action: Withhold idelalisib until Grade \leq 1. Recommended Action: Resume at lower dose level or discontinue idelalisib at investigator discretion.
Stevens-Johnson Syndrome (SJS)/Toxic Epidermal Necrolysis (TEN)	

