Grade 3 (ALT/AST $> 5\text{-}20\times$ ULN) (Bilirubin $> 3\text{-}10\times$ ULN)	
Recommended Action: Withhold idelalisib.
 
Required Action:
 
• Monitor ALT, AST, ALP, and bilirubin at least 1x per week until all abnormalities are Grade ≤ 1.• If bilirubin abnormality is Grade < 3, resume idelalisib at same dose level. If bilirubin abnormality is Grade ≥ 3, resume at lower dose level.
Grade 4 (ALT/AST $> 20\times$ ULN) (Bilirubin $> 10\times$ ULN)	
Required Action:
 
• Withhold idelalisib.• Monitor ALT, AST, ALP, and bilirubin at least 1x per week until all abnormalities are Grade ≤ 1.• If bilirubin abnormality is Grade 4, discontinue idelalisib. 
Recommended Action: If bilirubin abnormality is Grade < 4, resume study drug at lower dose level.

Pneumonitis (dyspnea, cough, hypoxia without obvious infectious cause)	
Grade ≤ 1	Recommended Action: Withhold idelalisib until resolution to baseline. May resume at lower dose level or discontinue idelalisib at investigator discretion.
Grade ≥ 2	
Required Action:
 
• Discontinue idelalisib. 
Recommended Action:
 
• Consider bronchoscopy to evaluate for PJP, CMV and other organisms (bacterial and viral)• Consider treatment with systemic corticosteroids.• Consider empiric treatment of pneumocystis if bronchoscopy is contraindicated• Upon resolution, may resume idelalisib at lower dose level at investigator discretion and /Gilead medical monitor agreement

NCI CTCAE Grade ^a	Idelalisib
Pneumocystis jirovecii pneumonia (PJP)	
Any Grade	Required Action: Discontinue idelalisib
Uequivocal CMV infection^c	
Any Grade	Required Action: 
Interrupt idelalisib upon unequivocal clinical or laboratory evidence of CMV infection.Treat according to established clinical guidelines.If the benefits of resuming idelalisib are judged to outweigh the risks, consideration should be given to administering pre-emptive CMV therapy.
Other Nonhematological Adverse Events	
Grade ≤ 2	Recommended Action: Maintain current dose level and schedule
Grade ≥ 3	Recommended Action: Withhold idelalisib until Grade ≤ 1 . May resume idelalisib at initial or lower dose level or discontinue idelalisib at investigator discretion.

a CTCAE, Version 4.03.

b See section [6.2](#) and [7.3.2](#) for additional requirements regarding an AE of diarrhea

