5.5. Discontinuation from Study

Subject study participation may be ended due to any of the follow reasons:

- Withdrawal of consent
- Objective evidence of disease progression.
- Unacceptable toxicity or unable to tolerate a second rechallenge for the same AE.
- Any subject who becomes pregnant or begins breastfeeding.
- Initiation of non-protocol specified anticancer therapy.
- Noncompliance with idelalisib administration, study procedures, or study requirements.
- The investigator may discontinue idelalisib, if it is not in the subject's best interest to continue.
- Any subject who is lost to follow-up.
- Death
- Discontinuation of study by the Sponsor, a regulatory agency, or an EC
- Any subject who is diagnosed with any grade SJS or TEN, Grade ≥ 2 pneumonitis, or any grade PJP.
- Any subject whose benefit-risk profile is not deemed positive by the investigator should discontinue study drug.

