7.3.5. Pulmonary Events

Documented bacterial, fungal, viral, and pneumocystis pneumonias have been observed in patients receiving idelalisib, primarily in patients with CLL. Some study subjects receiving idelalisib alone or in combination have developed evidence of pneumonitis without documented pulmonary infection.

Given the potential for infectious or drug-related pulmonary adverse events, clinicians should be particularly observant for evidence of respiratory events in subjects participating in this trial. Subjects who describe pulmonary symptoms (eg, dyspnea on exertion, cough, shortness of breath); manifest a decline from baseline of $\geq 5\%$ in oxygen saturation, or demonstrate evidence of pulmonary inflammation (eg, focal or diffuse interstitial pattern or ground-glass opacities on chest CT) should be evaluated. Potential bacterial, fungal, or viral etiologies should be assessed. Noninfectious etiologies such as pulmonary edema or thromboembolism should also be considered.

As appropriate for the clinical situation and culture results, subjects should be treated empirically or given specific antibiotics, antifungals, or antiviral agents for a cultured organism. Supportive care, including oxygen or mechanical ventilation, should be provided as necessary.

For subjects with suspected pneumonitis (eg, onset of cough, dyspnea, hypoxia and/or a diffuse interstitial pattern or ground-glass opacities on chest imaging without obvious infectious etiology), idelalisib should be interrupted (or discontinued if pneumonitis is Grade ≥ 2). Supportive care, including oxygen or mechanical ventilation, should be considered and provided as necessary. Consider bronchoscopy to evaluate for PJP, CMV and other organisms (bacterial and viral). Consider treatment with systemic corticosteroids. Consider empiric treatment of pneumocystis if bronchoscopy is contraindicated. Upon resolution, may resume idelalisib at lower dose level at investigator discretion and Gilead medical monitor agreement.

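### Table 5-2 requires idelalisib to be discontinued for Grade ≥ 2 pneumonitis and, in the same cell, allows it to be resumed, so it is unclear whether the stop is final

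*Protocol*

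**What the plan says.** Three parts of the protocol deal with Grade ≥ 2 pneumonitis.

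- **Section 5.2.10, Table 5-2.** In the Grade ≥ 2 row the required action is to "discontinue idelalisib". The last recommended action in that cell reads "Upon resolution, may resume idelalisib at lower dose level at investigator discretion and /Gilead medical monitor agreement". The Grade ≤ 1 row is separate and carries its own restart sentence: "Withhold idelalisib until resolution to baseline. May resume at lower dose level or discontinue idelalisib at investigator discretion".
- **Section 7.3.5.** For suspected pneumonitis, "idelalisib should be interrupted (or discontinued if pneumonitis is Grade ≥ 2"). The paragraph ends with a resume sentence almost identical to the one in the table, with no grade attached.
- **Section 5.5.** Among the reasons for which participation may be ended is "Any subject who is diagnosed with any grade SJS or TEN, Grade ≥ 2 pneumonitis, or any grade PJP".

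The text before Table 5-2 separates required from recommended actions and gives the second kind less force: "When a modification is indicated as a recommendation, it serves as a guideline".

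In the SAP, the treatment-emergent adverse event window (Section 7.1.5.1) closes 30 days after permanent discontinuation of study drug. The treatment-emergent laboratory window (Section 7.2.1.1) closes 30 days after the last dose for subjects who stopped permanently. Section 4.1 calls for a listing of reasons for premature discontinuation.

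**The concern.** A requirement to stop and a guideline permitting a restart cannot both govern the same event unless the protocol says that the stop is provisional, and it does not. An investigator who follows the required action, with Section 5.5 alongside, could reasonably treat the stop as final. One who follows the recommended action could ask the medical monitor to agree to a restart. Each could point to the protocol.

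What is at stake is first a re-exposure decision after a lung toxicity. The second issue is how data are classified: if nobody can say whether the stop was permanent, nobody can say when the SAP's windows close for that subject.

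**Working it through.** No figure in the plan bears on this point. There is no hypothesis test and no sample size calculation (SAP Section 1.3). The check is a comparison of texts.

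**Step 1. How Table 5-2 uses its terms.** These are all the rows that stop the drug:

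| Wording of the stop | Rows | Restart text in the row? |
|---|---|---|
| Withhold or interrupt | Neutropenia Grade 4; thrombocytopenia Grade 4; rash Grade ≥ 3; diarrhea/colitis Grade ≥ 3 or persistent Grade 2; hepatic Grade 3; hepatic Grade 4; pneumonitis Grade ≤ 1; CMV; other nonhematological Grade ≥ 3 | Yes, in all 9 |
| Discontinue, unconditionally | SJS/TEN; bowel perforation; PJP | No, in all 3 |
| Discontinue, unconditionally | Pneumonitis Grade ≥ 2 | Yes |

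The Grade ≥ 2 pneumonitis row is the only one that pairs an unconditional discontinuation with restart text. The hepatic Grade 4 row contains both ideas but assigns them to different bilirubin grades, so it does not conflict.

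**Step 2. Is discontinue just another word for withhold?** The table says not. In the rash, severe diarrhea, Grade ≤ 1 pneumonitis and other nonhematological rows, resuming and discontinuing are the two options after a hold. Section 5.2.9 likewise has the drug held and reinitiated, and discontinued only when rechallenge has failed. Section 7.1.3 lists interruption and discontinuation as different outcomes, and Section 7.3.5 contrasts them in one sentence.

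**Step 3. Could the restart text belong to Grade 1?** Not in the table, because Grade ≤ 1 has its own row and its own restart sentence. In Section 7.3.5 it could, because that paragraph covers both grades and the sentence names neither. If it does mean Grade 1 only, Section 7.3.5 and Table 5-2 disagree. If it covers Grade ≥ 2, Section 7.3.5 repeats the table's conflict. Either way the text needs aligning.

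**Step 4. What Section 5.5 adds.** It groups the event with two conditions whose table rows have no restart text, and it deals with failed rechallenge in a different bullet. That points towards a final stop, but its lead-in is permissive.

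**Step 5. Effect on the SAP.** Suppose a subject stops on day S and restarts on day R, with R later than S + 30. Consider an adverse event that starts between S + 30 and R and does not itself lead to discontinuation. If the stop on day S counts as permanent, the event is outside the treatment-emergent window. If it does not, the event is inside. The discontinuation-reason listing has the same ambiguity about whether day S is an entry. However, SAP Section 7.1.6 lists all adverse events and Section 4.2 lists dosing by subject, so a reader of the listings would see the event and the dates on either reading.

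**The case against.** The best defence is that the cell describes a stop followed by an agreed exception. The restart is conditional on resolution, a lower dose level, investigator discretion and medical monitor agreement; the Grade ≤ 1 row has no monitor condition. The protocol also knows how to say that a stop is irreversible: Section 5.3.2.1 uses the word permanently for PJP and never for pneumonitis. The restart bullet may well have been deliberate.

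Part of this stands. The monitor's agreement limits how far sites could diverge, and only two centers are planned. But it settles who approves a restart, not whether one is open after a required discontinuation. The missing adverb proves little, since the PJP row of the table also says only that the drug is discontinued. A recommendation that is a guideline cannot by itself override a requirement.

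A second defence is that Table 5-2 and Section 7.3.5 concern symptomatic or suspected pneumonitis, whereas Section 5.5 concerns a diagnosed event. That could ease the tension with Section 5.5. It does nothing for the conflict inside the cell.

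A reader might also infer three stronger things that the documents do not support:

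- **That a subject with this event must leave the study and has no route back to the drug.** Sections 5.5 and 3.5 both say only that participation may end. The Section 3.5 trigger, "The subject permanently discontinues idelalisib treatment for any reason", presupposes the permanence that is in question. The mandatory withdrawal text in Section 6.3 speaks of unacceptable toxicity and does not name pneumonitis.
- **That exclusion criterion 2 contradicts the restart.** It gives "history of drug-induced pneumonitis, ongoing inflammatory bowel disease" as examples of toxicities that preclude starting idelalisib. That is an entry rule and does not govern rechallenge during treatment.
- **That one case would distort a third of the safety data.** The arithmetic (1 of 3) is trivial, but the documents report no pneumonitis case and give no incidence for this study, so it does not measure the effect.

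**Conclusion.** The inconsistency is real and sits chiefly in one cell of Table 5-2; Sections 7.3.5 and 5.5 are related text that does not resolve it. It is a conflict of wording in toxicity management, and it matters because it concerns re-exposure after a lung toxicity.

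Its statistical size is small. The study has no primary endpoint and no hypothesis, 3 subjects were enrolled, and the SAP plans by-subject listings. Only a subject with Grade ≥ 2 pneumonitis would be affected, and a treatment-emergent flag would change only in the restart pattern described above.

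The conclusion assumes that discontinue carries in this row the sense it has in the rest of the table. If the sponsor meant something else here, the row has to say so. No view is taken on which clinical rule is right.

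**What to change.** The sponsor should decide which outcome applies to Grade ≥ 2 pneumonitis and make three places state it:

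1. **Table 5-2, Grade ≥ 2 pneumonitis row:** the required and recommended actions must agree on whether the stop is final.
2. **Section 7.3.5:** say which grades the resume sentence covers.
3. **Section 5.5:** word the pneumonitis item so that it fits the chosen outcome.

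For analysis, one sentence in the SAP should say whether a stop followed by a restart counts as permanent discontinuation for the treatment-emergent windows and as an entry in the discontinuation-reason listing. The documents do not say whether any subject is still on treatment. If none is, the clinical study report should state which rule was applied.

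The cost is a short protocol wording change, a letter to the sites and one line in the SAP. No procedure, visit or data item is added.

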5.3. Prior and Concomitant Medications

If considered necessary for the subject's well-being, drugs for concomitant medical conditions or for symptom management may be given at the discretion of the investigator.

Any concomitant medications prescribed as a therapeutic intervention for or resulting in an AE or SAE during the course of the study and the reason for use should be recorded on the eCRFs.

5.3.1. Anticancer or Experimental Therapies Other than Investigational Treatments

Except for corticosteroids, no other anticancer therapies (including chemotherapy, radiation, antibody therapy, immunotherapy, or other experimental therapies) of any kind are permitted. Subjects are not allowed to participate concurrently in any other therapeutic clinical study.

5.3.2. Antibiotics/ PJP Prophylaxis

5.3.2.1. Infectious Events

Patients with lymphoid cancers receiving idelalisib have developed serious and fatal infections during therapy. Opportunistic infections, most notably *Pneumocystis jirovecii* pneumonia (PJP) and CMV infection, have most frequently occurred within the first 6 months of treatment with idelalisib and are increased in the context of concurrent myelosuppressive therapy such as bendamustine.

Subjects must receive trimethoprim-sulfamethoxazole or other established prophylaxis for PJP throughout the course of idelalisib treatment, and for 2 to 6 months following the last dose of idelalisib. Prophylaxis must continue until the CD4+ T-cell count is documented to be >200 cells/mcL after idelalisib treatment ends. Subjects must permanently discontinue idelalisib upon diagnosis of PJP.

CMV surveillance for active disease (quantitative PCR or PP65 antigen) must be conducted approximately every 4 weeks throughout the course of idelalisib treatment. CMV viral load testing should be performed from the same specimen type whenever possible and caution should be exercised when comparing CMV viral load results across different testing centers. If unequivocal clinical or laboratory evidence of CMV infection is present, the subject must interrupt idelalisib treatment and undergo effective antiviral treatment according to established clinical guidelines. If the benefits of resuming idelalisib are judged to outweigh the risks, consideration should be given to administering pre-emptive CMV therapy.

In high-risk subjects (history of recurrent infection, allogeneic transplant, treatment with alemtuzumab, hypogammaglobulinemia) other infection prophylaxis should be considered per consensus guidelines. Administration of intravenous immunoglobulin is permitted per standard institutional practice {[Raanani et al 2009](#)}. For subjects who develop an infection, appropriate medical therapy should be instituted in a timely manner.

Trimethoprim sulfamethoxazole is rated a Pregnancy category C agent. In rats, oral doses of 533 mg/kg or 200 mg/kg produced teratologic effects manifested mainly as cleft palates. One survey found no congenital abnormalities in 35 children whose mothers had received oral sulfamethoxazole and trimethoprim at the time of conception or shortly thereafter. Because sulfamethoxazole and trimethoprim may interfere with folic acid metabolism it should be used during pregnancy only if the potential benefit justifies the potential risk to the fetus.

Dapsone is rated a Pregnancy Category C agent. Extensive, but uncontrolled experience and two published surveys on the use of Dapsone in pregnant women have not shown that Dapsone increases the risk of fetal abnormalities if administered during all trimesters of pregnancy or can affect reproduction capacity. Because of the lack of animal studies or controlled human experience, Dapsone should be given to a pregnant woman only if clearly needed. Dapsone is excreted in breast milk in substantial amounts. Hemolytic reactions can occur in neonates. Because of the potential for tumorigenicity shown for Dapsone in animal studies a decision should be made whether to discontinue nursing or discontinue the drug taking into account the importance of drug to the mother.

Atovaquone is rated a Pregnancy Category C agent. Atovaquone is teratogenic and did not cause reproductive toxicity in rats at plasma concentrations up to 2 to 3 times the estimated human exposure. Atovaquone can cause maternal toxicity in rabbits at plasma concentrations that were approximately one half the estimated human exposure. Mean fetal body lengths and weights were decreased and there were higher numbers of early resorption and post-implantation loss per dam. It is not clear whether these effects are caused by atovaquone directly or are secondary to maternal toxicity. Concentrations of atovaquone in rabbit fetuses averaged 30% of the concurrent

maternal plasma concentrations. There are no adequate and well-controlled studies in pregnant women. Atovaquone should be used during pregnancy only if the potential benefit justifies the potential risk to the fetus. It is not known whether atovaquone is excreted into human milk. Because many drugs are excreted into human milk, caution should be exercised when Atovaquone is administered to a nursing woman. In a rat study, atovaquone concentrations in the milk were 30% of the concurrent atovaquone concentrations in the maternal plasma.

Aerosolized Pentamidine (NebuPent) is a Pregnancy Category C agent. There are no adequate and well controlled studies of NebuPent in pregnant women. One literature report indicated that intravenously administered pentamidine in pregnant rats at 4 mg/kg/day was embryolethal; teratogenicity was not observed in this study. It is unknown whether pentamidine administered via the aerosolized route crosses the placenta at clinically significant concentrations. It is not known whether NebuPent can cause fetal harm when administered to a pregnant woman. NebuPent should be given to a pregnant woman only if clearly needed. It is not known whether NebuPent is excreted in human milk. NebuPent should not be given to a nursing mother unless the potential benefits are judged to outweigh the unknown risks.

5.3.3. Antidiarrheals

As needed, subjects may be prescribed loperamide (Imodium® or others) or diphenoxylate and atropine (Lomotil®) to control diarrheal symptoms.

